10. SCHEDULE OF PROCEDURES

[figure not shown]
10.1. Screening Period (Days - 30 to -1)

[figure not shown]
Subjects will complete the following procedures after fasting for at least 10 hours prior to clinical laboratory assessments.

[figure not shown]
The magnetic resonance imaging procedures may be completed at any time during the screening period. If a subject is washing out of prohibited medication, the imaging must be performed after the washout has been completed. Use of NSAIDs or acetaminophen within 24 hours of imaging visit is prohibited.

[figure not shown]
- ICF
- Eligibility: inclusion/exclusion

[figure not shown]

[figure not shown]

[figure not shown]

11. INDIVIDUAL STOPPING CRITERIA

Subjects will be withdrawn from the treatment period of the study if the following laboratory results are confirmed by repeat testing. Repeat testing must be completed within 48-72 hours:

12. STATISTICS

12.1. Sample Size Determination

The sample size was based on clinical considerations rather than statistical power.

12.2. Statistical Analysis Plan

Detailed methodology for summary and statistical analyses of the data collected in this study will be documented in a statistical analysis plan (SAP), which will be finalized before the study has completed. Additional statistical analyses other than those described in this section may be performed if deemed appropriate and will be described in the SAP.

Descriptive statistics for categorical endpoints will include the number and percent of subjects in each category. Quantitative endpoints will be summarized with the mean, median, standard deviation, minimum value, and maximum value.

All data will be displayed in individual subject listings.

12.3. Analysis Populations

The safety population will consist of all subjects who receive at least 1 dose of study drug, whether NYX-2925 or placebo.

The efficacy population will consist of all subjects in the safety population with MRI measurements at baseline and following treatment with placebo and NYX-2925 20 mg.

12.4. Accountability and Baseline Characteristics

The number and percent of subjects who are treated with study drug, prematurely discontinue, and complete the study will be summarized. The number and percent of subjects will be summarized for each reason for premature discontinuation, overall and by study period.

Demographic data will be summarized descriptively for each analysis population.

12.5. Analyses of Efficacy

The following changes in efficacy endpoints will be summarized descriptively:

- Change from baseline to each scheduled evaluation after baseline, with baseline defined as the last evaluation prior to dosing with study drug on Day 1.
- Change from end of the placebo period to scheduled evaluations during each NYX-2925 period.
- Change from end of each NYX-2925 period to scheduled evaluations during the placebo follow-up period

Change to scheduled evaluations will be assessed with the paired t-test and signed rank test.

12.6. Analyses of Safety

All safety summaries will be descriptive; no statistical testing will be performed.

12.6.1. Adverse Events

A treatment-emergent AE (TEAE) is defined as an AE with an onset that occurs after receiving study drug, or a continuing AE diagnosed prior to the date of first dose of study drug, which increases in severity after the start of dosing. Adverse events will be categorized by system organ class and preferred term with the Medical Dictionary for Regulatory Activities.

Summary tables for TEAEs will include numbers and percentages of subjects experiencing TEAEs by system organ class and preferred term. If a subject has more than 1 TEAE that codes to the same preferred term, the subject will be counted only once for that preferred term. Similarly, if a subject has more than 1 TEAE within a system organ class category, the subject will be counted only once in that system organ class category.

The following TEAE summaries will be provided for each study period (placebo, NYX 2925 20 mg, NYX-2925 200 mg, and follow-up:

- Overall summary of TEAEs,
- TEAEs by system organ class and preferred term,
- Drug-related TEAEs by system organ class and preferred term,
- TEAEs by system organ class, preferred term, and severity.

Serious TEAEs, and TEAEs leading to study drug discontinuation will be identified.

12.6.2. Clinical Laboratory Tests

Clinical laboratory results considered clinically important by the investigator will be identified.

Individual results of clinical laboratory tests from hematology, serum chemistry, and urinalysis outside of the normal range will be flagged in the data listings.

12.6.3. ECG

ECG results considered clinically important by the investigator will be identified.

12.6.4. Vital Sign Measurements

Change from baseline to each scheduled measurement will be summarized descriptively. Baseline will be defined as the last evaluation prior to dosing with study drug on Day 1.

12.6.5. Other Safety Data

Clinically significant deteriorations in physical examination will be recorded as adverse events.

12.6.6. C-SSRS

Subjects with suicidal ideation will be identified. Suicidal ideation will be defined as a “yes” answer at any time after the first dose of study drug to any of the 5 suicidal ideation questions on

the C-SSRS. Data collected for C-SSRS will be summarized by treatment and visit/time point. Change from Baseline, if applicable, will also be calculated and summarized in the same manner.

12.6.7. Interim Analysis

Interim analyses may be completed for this study. Given that the study is single-blind and Phase 2, there will be no adjustments to Type I error.

13. ADMINISTRATIVE

13.1. Source Documents

Source documents are defined as the result of original observations and activities of a clinical investigation. Source documents may include, but are not limited to, study progress notes, e-mail correspondences, ICFs, clinical laboratory reports, imaging results, medical histories, hospital records, and drug accountability records. All source documents will be maintained by the investigator(s) and made available for inspection by sponsor representatives, the FDA, and other applicable regulatory authorities.

13.2. Study Monitoring

Site visits will be conducted by an authorized sponsor representative (site monitor) to inspect study data, source documents, and eCRFs in accordance with the International Council for Harmonisation of Technical Requirements for Pharmaceuticals for Human Use (ICH) guidelines, good clinical practices (GCPs), and local regulations or guidelines. The monitor will inspect the study data at regular intervals throughout the study to verify adherence to the protocol, as well as completeness, consistency, and accuracy of study data.

The investigator will permit sponsor representatives, its third party vendors, the FDA, and/or respective health authorities to inspect facilities and records relevant to this study.

13.3. Case Report Forms

An eCRF will be used to record all subject data required in this protocol. The eCRF must be completed by designated and trained study personnel. The eCRF will be signed by the principal investigator or a subinvestigator listed on the FDA Form 1572. It is the responsibility of the principal investigator to ensure the eCRFs are completed and submitted to Aptinyx (or designee) in an accurate and timely manner. The processing of eCRFs will include an audit trail (to include changes made, reason for change, date of change and person making the change).

13.4. Protocol Amendment(s)

If a protocol has been filed with regulatory agencies or submitted to an IRB and requires changes, a protocol amendment must be written. The sponsor will make changes to the protocol. All amendments will be sent to a central IRB on the study sites' behalf, if applicable. Sites using a local IRB are responsible for submitting the amendment for review and approval.

13.5. Audits and Inspections

During the course of the study, or after completion of the study, each study site may be subject to an audit by an Aptinyx Quality Assurance auditor (or an auditor appointed by Aptinyx or its authorized representative) and/or an inspector from the FDA and/or other regulatory authority. Every attempt will be made to notify the investigator in writing in advance of the audit.

13.6. Institutional Review Board/Independent Ethics Committee (IRB/IEC)

This protocol, the informed consent document, and all relevant supporting data must be submitted to the IRB for approval. IRB approval of the protocol, informed consent document, any subject facing material, and any advertisement used to recruit study subjects must be obtained before the study may be initiated. The IRB must comply with requirements set forth in the Code of Federal Regulations (CFR) part 56.

The investigator is responsible for keeping the IRB advised of the progress of the study, changes to research activity, unanticipated problems involving risk to human subjects or others, and any changes made to the protocol as deemed appropriate, but in any case, at least once a year. The investigator is also responsible for notifying the IRB of any significant AEs or protocol deviations that occur during the study, and meet IRB reporting requirements.

The investigator agrees that he or she will not make any changes in the research without IRB approval, except where necessary to eliminate apparent immediate hazards to human subjects, as referenced in 21 CFR 312.66.

13.7. Compliance with Regulatory Requirements

This protocol will be conducted in compliance with the protocol and all regulatory requirements, in accordance with GCP, including ICH Guidelines, and in general conformity with the most recent version of the Declaration of Helsinki.

13.8. Informed Consent

Written informed consent must be obtained from potential study participants prior to the initiation of non-routine study-related tests. The original signed ICF for each participating subject shall be filed with records kept by the investigator(s). A copy of the signed informed consent document must be provided to the subject. If applicable, written consent will be obtained using a certified translation. If the ICF is revised, subjects must be re-consented in a timely manner.

13.9. Study File Management

The investigator is responsible for ensuring that the study files are maintained. The study file will include, but is not limited to, source documents, correspondence, regulatory documents (IRB approvals/correspondence, study logs, FDA 1572 forms, financial disclosures, clinical study material records, IP accountability records, medical records).

13.10. Study Completion

Aptinyx requires the following data and materials be completed before a study can be considered terminated or completed: source documents are completed, IP reconciliation activities are completed, study procedures and assessments are completed and source verified.

13.11. Confidentiality

Personal study subject data collected and processed for the purposes of this study should be managed by the investigator and his/her staff with adequate precautions to ensure the confidentiality of personal health information (PHI), and in accordance with applicable national and/or local laws and regulations on PHI protection.

Monitors, auditors, and other authorized agents of Aptinyx, the IRB approving this research and applicable regulatory authorities will be granted direct access to the study subjects' original medical records for verification of clinical study procedures and/or data, without violating the confidentiality of the subjects, to the extent permitted by the law and regulations. In any presentation of the results of this study at meetings or in publications, the subjects' identity will remain confidential.

13.12. Compensation, Insurance, and Indemnity

Information regarding compensation, insurance, and indemnity is addressed in the Clinical Trial Agreement.

13.13. Financial Disclosure

The investigator(s) are responsible for providing financial disclosure(s) in covered clinical studies. Principal investigators and subinvestigators are required to disclose applicable financial information, and to promptly update Aptinyx with any relevant changes throughout the study and for 1 year after study completion.

13.14. Records Retention

According to US Investigational New Drug regulations (21 CFR 312.62), records and documents pertaining to the conduct of this study and the distribution of IPs including but not limited to source documents, eCRFs, ICFs, clinical laboratory test results, and drug inventory records will be retained. These records will be kept on file by the principal investigator for 2 years after a marketing application is approved for the drug for the indication for which it is being studied. If no application is filed or approved, these records must be kept for 2 years after the investigation has been discontinued and the FDA has been notified. Per ICH guidelines, documents should be retained until at least 2 years after the last approval of a marketing application in an ICH region and until there are no pending or contemplated marketing applications in an ICH region, or at least 2 years have elapsed since the formal discontinuation of clinical development of the IP. Aptinyx will notify the investigator when records and documents no longer need to be retained. No study records should be destroyed without prior authorization from Aptinyx.

13.15. Publication Policy

The publication policy is outlined in the Clinical Trial Agreement.

This statistical analysis plan (SAP) describes the planned statistical analysis and reporting of the clinical study protocol titled “A Phase 2, Single-Blind, Exploratory, Placebo-controlled, Pilot Study to Assess the Efficacy and Safety of Daily Oral NYX-2925 in Subjects with Fibromyalgia” dated on March 7, 2018, amendment #3.

The structure and content of this SAP provides sufficient detail to meet the requirements identified by the US Food and Drug Administration (FDA), European Medicines Agency (EMA), and International Conference on Harmonisation (ICH) of Technical Requirements for Registration of Pharmaceuticals for Human Use: Guidance on Statistical Principles in Clinical Trials^[1]. All work planned and reported for this SAP will follow internationally accepted guidelines, published by the American Statistical Association^[2] and the Royal Statistical Society^[3], for statistical practice.

The purposes of this SAP are to:

- Outline the types of analyses and presentations of data that will form the basis for drawing conclusions to the study objectives and hypotheses outlined in the protocol
- Explain in detail how the data will be handled and analyzed, adhering to commonly accepted standards and practices for Good Statistical Practice

All analyses described in this plan are considered *a priori* analyses in that they have been defined prior to performing any interim analyses. The planned analyses identified in this SAP may be included in clinical study reports (CSR), regulatory submissions, or future manuscripts. Also, post-hoc exploratory analyses not identified in this SAP may be performed to further examine study data. Any post-hoc or unplanned exploratory analyses performed will be clearly identified as such in the final CSR.

The following documents were reviewed in preparation of this SAP:

- [REDACTED]
- [REDACTED]
- [REDACTED]

- [REDACTED]
- [REDACTED]

The reader of this SAP is encouraged to also read the clinical study protocol and other identified documents for details on the planned conduct of this study. Operational aspects related to collection and timing of planned clinical assessments are not repeated in this SAP unless relevant to the planned analyses.

3. Study Objectives

3.1 Primary Objective

The primary objective of this study is to determine whether daily dosing with NYX-2925 20 or 200 mg changes the markers of central pain processing in subjects with fibromyalgia using functional magnetic resonance imaging (fMRI), resting state functional connectivity magnetic resonance imaging (rs-fcMRI) and proton magnetic resonance spectroscopy (¹H-MRS) on active drug versus placebo.

nd
ain

3
3

4. Study Overview

4.1 Study Design and Study Drug Treatment Periods

This is a single-blind, exploratory, placebo-controlled, pilot study to assess the efficacy and safety of daily oral NYX-2925 in fibromyalgia subjects. The study includes a screening period (up to 30 days), a placebo period, an active treatment period with 2 dose strengths, and a follow-up period as follows:

- Placebo PO QD for 2 weeks
- NYX-2925 20 mg PO QD for 2 weeks
- NYX-2925 200 mg PO QD for 2 weeks
- Follow-up for 1 week

The schedule of assessments is provided in in [Appendix I](#).

4.2 Subject Randomization

This study does not require a randomization because the treatment periods are fixed.

4.3 Number of Subjects

The protocol for this study planned on enrolling approximately 24 subjects at 2 study sites in the United States.

4.4 Sample Size Considerations

The sample size for this pilot study was based on practical, clinical considerations rather than a formal determination of statistical power.

4.5 Unblinding Study Drug Treatment Procedures

Not applicable because this is not a double-blind or randomized study.

4.6 Analyses Changes from the Protocol

In Section 12.6.1 of the protocol, it states that TEAE summaries will be provided separately for each study period and the follow-up period. TEAEs will be summarized and grouped based on the last study drug treatment the subject received compared to the start date of the event explained in [Section 5.2](#). The rest of the analyses stated in the protocol support the analyses planned in this SAP.

5. General Statistical Principles

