9.5.2. Recording Adverse Events

A "pre-existing" condition is one that is present before study drug dosing and is reported as part of the subject's medical history. Pre-existing conditions should be reported as an AE only if the frequency, intensity, or character of the pre-existing condition worsens during the course of the study. Adverse events will be collected from the time the informed consent is signed to the end of the subject's participation in the study.

Subjects should be instructed to report all potential AEs to the investigator, and, queried in a non-leading manner, without specific prompting (e.g., "How are you feeling?"). The site study staff should assess emerging symptoms of dissociative reaction similar to those caused by NMDA antagonists including memory impairment, disturbance in time, body or environmental perception, stilted speech, emotional withdrawal, impaired coordination, motor retardation, bizarre reasoning or illusory experiences in any sensory perception, or confused state; such symptoms may be captured as AEs.

To avoid vague, ambiguous, or colloquial expressions, all AEs should be recorded in standard medical terminology rather than in the subject's own words. Each AE will also be described in terms of duration (start and stop date), severity, relationship to IP, relationship to study procedure, action(s) taken, and outcome. Diagnoses (rather than symptoms) should be recorded wherever possible.

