5.2 Treatment Allocation

Subjects are planned to receive multiple study drug treatments in the study. Therefore, the following treatments will be assigned during these periods:

- Screening Visit until 1 Day Prior to the Day 1 (Baseline) Visit: No Treatment
- Day 1 (Baseline) Visit until the Week 2 Visit: [REDACTED]
- 1 Day After Week 2 Visit until the Week 4 Visit:
 - If any adverse events and/or concomitant medications start on the Week 2 visit, then those records will be assigned to the [REDACTED] treatment arm.
- 1 Day After Week 4 Visit until the Week 6 Visit:
 - If any adverse events and/or concomitant medications start on the Week 4 visit, then those records will be assigned to the [REDACTED] treatment arm.
- 1 Day After Week 6 Visit until the Follow-Up (Week 7) Visit: [REDACTED]
- Unscheduled or Early Termination Visits: Last Study Drug Dispensed and Taken

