5.3 Treatment Group Comparisons

The following treatment groups will be summarized in the statistical tables:

- Placebo
- NYX-2925 20 mg PO QD
- NYX-2925 200 mg PO QD
- All Doses of NYX-2925
 - Pooled for adverse events, concomitant medications, and study drug treatment compliance and exposure tables.
- Not Treated
 - This will only be displayed for the analysis population table that presents subjects screened, but were not enrolled in the study or dispensed study drug.
- All Subjects
 - This will only be displayed for the analysis population and concomitant medications tables.

The following changes in treatment period comparisons will be performed for efficacy:

- Change from Baseline
- Change from Week 2 [REDACTED]
- Change from Week 4 [REDACTED]
- Change from Week 6 [REDACTED]

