8.1 Study Drug Accountability

Subjects will be dispensed study drug based on fixed treatment periods at visits Day 1 (Baseline), Week 2, and Week 4. In the event the subject comes in for an unscheduled visit prior to a weekly visit, they may be dispensed additional study drug. Additional study drug may be dispensed at any study visit or unscheduled visit if the subject will need study drug beyond the two week allotment

provided at Day 1, Week 2 and Week 4. Capsule strengths for NYX-2925 are 10 mg and 100 mg. Subjects will be instructed to take 2 capsules of investigational product once daily by mouth.

The following data will be collected and derived at each start and end to the study drug accountability treatment periods/visit intervals:

Parameter	Origin/Derivation
Capsules Dispensed Amount	CRF
Capsules Returned Amount	CRF
Expected Number of Capsules Taken	Derived: Date Returned – Date Dispensed + 1 (where the maximum would be 30 because 30 capsules are issued at each dispensing visit)
Estimated Number of Capsules Taken	Derived: Number of Capsules Dispensed Amount – Number of Capsules Returned Amount
Treatment Compliance (%)	Derived: $100 \times \frac{\text{Estimated Number of Capsules Taken}}{\text{Expected Number of Capsules Taken}}$ (rounded off by one number after the decimal point)

The Overall NYX-2925 Treatment Compliance (%) will be calculated as:

- $100 \times \frac{\sum (\text{Estimated Number of Capsules Taken at All Study Drug Return Visits After NYX-2925 20 mg or 200 mg PO QD was Dispensed})}{\sum (\text{Expected Number of Capsules Taken at All Study Drug Return Visits After NYX-2925 20 mg or 200 mg PO QD was Dispensed})}$ and rounded off by one number after the decimal point

A subject will be classified as being compliant with study drug administration if their calculated compliance by each treatment period and overall is between 80% and 125%, inclusive. Descriptive statistics will be summarized for treatment compliance by returning analysis visits Week 2 (Placebo), Week 4 (NYX-2925 20 mg PO QD), Week 6 (NYX-2925 200 mg PO QD), and Overall (NYX-2925 20 mg and 200 mg PO QD). The following categorical ranges will be summarized in a table for those same analysis visits and overall:

- <80%, 80-125%, >125%, and Not Reported

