12.1 Adverse Events

Treatment-emergent adverse events (TEAEs) will be those occurring during or after administration of the first dose of study drug until 30 days after the final dose of study drug. The date and time of first dose of study drug was not collected on the CRF for all subjects. Therefore, the following algorithm will be used to determine if the adverse events are treatment-emergent without a date and time of first dose of study drug:

- Earliest Possible AE Start Date \geq Day 1 (Baseline) Visit and Study Drug Dispensation **and**
- Latest Possible AE Start Date \leq 30 Days After the Final Dose of Study Drug

AEs that started prior to first dosing of study drug, but become worse in severity after receiving study drug will be considered treatment-emergent. The determination of whether or not an adverse event is classified as “treatment emergent” (i.e. TEAE) is not determined by the classification of “relationship

to study drug" collected on the CRF, but rather by the temporal relationship of the adverse event to the administration of study drug.

A related study drug TEAE is defined as any TEAE with at least a possible relationship to the study drug as assessed by the investigator or that is missing the assessment of causal relationship whose relationship to the study drug could not be ruled out. Relationships of "possibly related", "probably related", or missing are collected on the CRF, then those adverse events will be considered related study drug TEAEs. If the "unrelated" or "unlikely related" are collected on the CRF, then those adverse events will be considered not related study drug TEAEs.

Severity is assigned to each adverse event collected on the CRF. Maximum severity has the following order: "life threatening", "severe", "moderate", and "mild" as possible collection options on the CRF. A missing severity will be treated as "unknown" for analysis purposes.

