All adverse events will be coded and summarized by System Organ Class (SOC) and Preferred Term (PT) based on Medical Dictionary for Regulatory Activities (MedDRA) version 19.0 coding dictionary. This data will be summarized in a frequency distribution. Subjects may have more than one TEAE record per SOC and PT. At each level of subject summarization, a subject will be counted once if he/she reports one or more TEAE record at that specific level. For tables summarized by SOC and PT, the events will be displayed in the order of descending frequency counts for all treatments by SOC and then PT within SOC.

The number of subjects with at least one of the following adverse events, percentages for each category by treatment, and the number of total events will be included in an overall treatment-emergent adverse events summary table:

- Any TEAEs
- Related TEAEs
- Maximum Severity TEAEs
- Serious TEAEs
- Related, Serious TEAEs
- TEAEs Leading to Study Discontinuation
- Related TEAEs Leading to Study Discontinuation
- TEAEs Leading to Death

[figure not shown]
Summaries including the number of subjects and percentages of the following adverse events by SOC and PT will be provided:

- Any TEAEs
- Related TEAEs
- Maximum Severity TEAEs
- Serious TEAEs
- TEAEs Leading to Study Discontinuation

Additionally, TEAEs will be summarized by descending frequency counts of PT for all treatments. All adverse event data collected will be provided in subject listings. Subset subject listings will also be provided by serious treatment-emergent adverse events and deaths; by treatment-emergent adverse events leading to study discontinuation; any adverse events that are not considered to be treatment-emergent; by serious adverse events and deaths that are not considered to be treatment-emergent; and by adverse events leading to study discontinuation that are not considered to be treatment-emergent.

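### SAP 4.6 drops the protocol's separate follow-up TEAE summary; the visible text implies that follow-up events count under 200 mg, giving it nominally 21 days of capture against 14 for placebo

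*SAP*

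**What the plan says.** Protocol 12.6.1 sets out the tables by period: "The following TEAE summaries will be provided for each study period (placebo, NYX 2925 20 mg, NYX-2925 200 mg, and follow-up". SAP 4.6, which lists departures from the protocol, cites that plan and replaces it: "TEAEs will be summarized and grouped based on the last study drug treatment the subject received compared to the start date of the event". It refers to SAP 5.2 for the details and gives no reason in the visible text.

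SAP 5.2 has a separate entry for the interval "1 Day After Week 6 Visit until the Follow-Up (Week 7) Visit", but the treatment label beside it is blacked out. After early termination, it assigns the last drug dispensed and taken. The columns in SAP 5.3 are placebo, 20 mg, 200 mg, all doses of NYX-2925, not treated and all subjects, with no follow-up column. The all-doses column is described as "Pooled for adverse events, concomitant medications, and study drug treatment compliance and exposure tables".

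On supply, SAP 8.1 states: "Subjects will be dispensed study drug based on fixed treatment periods at visits Day 1 (Baseline), Week 2, and Week 4" (extra supply is possible if a subject needs it beyond the two-week allotment). On timing, SAP 12.1 counts events during or after administration "of the first dose of study drug until 30 days after the final dose of study drug". Under protocol 9.5.2, "Adverse events will be collected from the time the informed consent is signed to the end of the" subject's participation.

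On the measure, SAP 12.1 gives the number of subjects, "percentages for each category by treatment, and the number of total events will be included in an overall treatment-emergent adverse events summary table". SAP 5.4.2 bases percentages on numbers of subjects.

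**The concern.** For a completer, the last study drug received is 200 mg, and follow-up falls inside the TEAE window. Under the 4.6 rule, the follow-up week is therefore added to the 200 mg column. That column then collects events for half as long again as placebo, while both percentages are taken over subjects, not time. With no drug effect at all, 200 mg would tend to show more subjects with events than placebo or 20 mg. The pattern would look like a dose-related rise, and the summary table would not show how much of it came from follow-up.

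Safety is the secondary objective (protocol 5.2), and protocol 6.2 describes this as the first study of the drug in fibromyalgia. The between-period TEAE table is likely to be what most readers consult.

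**Working it through.** The documents give no AE risk or capture time to reproduce, so the check has two parts: capture time from the stated schedule, then an illustration under assumed risks.

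**1. Where follow-up events go**

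| Text | What it implies for a completer |
|---|---|
| SAP 4.6: last drug received before event onset | 200 mg after Week 4 |
| SAP 8.1: scheduled dispensing at Day 1, Week 2, Week 4 | no new drug after the 200 mg period |
| SAP 12.1: window to 30 days after final dose | follow-up events are TEAEs |
| SAP 5.3: column list | no separate place for them |
| SAP 5.2: label after Week 6 | redacted; cannot confirm or refute |

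One phrase points the other way: protocol 12.5 refers to follow-up as a placebo period.

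**2. Nominal capture for completers** (periods of 2, 2, 2 and 1 weeks, SAP 4.1)

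| | Placebo | 20 mg | 200 mg | Follow-up |
|---|---|---|---|---|
| Protocol 12.6.1 | 14 d | 14 d | 14 d | 7 d |
| SAP, follow-up under 200 mg | 14 d | 14 d | 14 + 7 = 21 d | – |
| SAP, if the label were placebo | 14 + 7 = 21 d | 14 d | 14 d | – |

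In the second row, 200 mg to placebo is 21/14 = 1.5. After early termination, the extra time goes to whichever drug was last taken, so 1.5 describes completers.

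**3. Effect on percentages with no drug effect**

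Assumptions, none from the documents: a two-week risk p of 10%, 20% or 30%; constant hazard on treatment; and a follow-up-week hazard half to equal that on treatment. The 200 mg column then has 14 + 3.5 = 17.5 to 14 + 7 = 21 equivalent days, and the risk over d days is 1 − (1 − p)^(d/14).

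| p (placebo) | 200 mg, 17.5 d | 200 mg, 21 d |
|---|---|---|
| 10% | 1 − 0.9^1.25 = 12.3% | 1 − 0.9^1.5 = 14.6% |
| 20% | 1 − 0.8^1.25 = 24.3% | 1 − 0.8^1.5 = 28.4% |
| 30% | 1 − 0.7^1.25 = 36.0% | 1 − 0.7^1.5 = 41.4% |

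At p = 20% with the planned 24 subjects, placebo is 24 × 0.20 = 4.8, and 200 mg is 24 × 0.243 = 5.8 to 24 × 0.284 = 6.8. The excess is about 1 to 2 subjects.

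**4. The pooled column, kept apart**

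Combining two active periods already gives 28 days: 1 − 0.8² = 36.0%, or 16.0 points above placebo. Adding follow-up gives 39.5% (31.5 d) to 42.8% (35 d), so follow-up contributes 3.5 to 6.8 of a total excess of 19.5 to 22.8 points.

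**5. What subject-weeks would show** (24 completers)

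Last-drug grouping: placebo 24 × 2 = 48, 20 mg 48, 200 mg 24 × 3 = 72, pooled 120. With follow-up separate: 48, 48, 48, follow-up 24, pooled 96.

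**The case against.** The change is openly declared, and attribution to the last drug received is a legitimate view: an event soon after the last 200 mg dose may well belong to that dose. The safety tables are descriptive and untested (SAP 5.4.3), and no visible decision rule depends on them. Start and stop dates are recorded and all events are listed, so follow-up events can be traced. Fixed period order confounds drug with time in any case. All of this stands and keeps the point small. It does not explain why the planned split should go.

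The assignment to 200 mg is an inference. The redacted SAP 5.2 entry is separate from the 200 mg entry, and protocol 12.5 could suggest a placebo label. That also stands, but any listed treatment column given the extra week ends up with unequal capture.

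The planned table list in SAP 15 is unreadable and the shells are a separate document, so a split or footnote may exist there. The claim therefore covers only the readable text.

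SAP 8.2 already summarises days of exposure by treatment period, and SAP 5.3 pools the exposure tables. This shows the longer dosing time behind the pooled column, but exposure stops at the last dose and does not cover the follow-up week.

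Two stronger readings are tempting and should not be drawn:
- A reader might blame the whole pooled excess on SAP 4.6. Most of it, 16.0 points in the illustration, comes from the SAP 5.3 pooling and would remain after this fix.
- Protocol 9.5.7 runs SAE reporting to 30 days after the last dose, so a reader might conclude that serious TEAEs get 14 + 30 = 44 days under 200 mg against 14 for placebo (44/14 = 3.1). That is only a possible consequence of 4.6: the visible 5.2 interval ends at the Week 7 visit, and serious events also have their own listings.

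**Conclusion.** The point holds, as something to consider rather than a serious fault. The readable text removes the protocol's follow-up TEAE summary and implies nominal capture of 14, 14 and 21 days for placebo, 20 mg and 200 mg, a ratio of 1.5, with no time adjustment in the TEAE section. The likely size is one to two of 24 subjects if the two-week risk is 20%; that risk and the follow-up hazard are assumed. The direction depends on the redacted label: if it reads placebo, placebo has the longer capture. Confidence is medium for that reason. The documents do not support a claim that the SAP states the 200 mg assignment outright, that the change was concealed, or that any safety test is biased.

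**What to change.** In the TEAE tables:
- Show events starting after the Week 6 visit in a separate follow-up column, as protocol 12.6.1 planned.
- For subjects who stop early, show events starting after the last dose in the same column, so that post-dose time does not return to the treatment columns.
- Keep a last-drug tabulation as a second view if wanted.
- Add a line with subject-weeks of observation to every column, including pooled.
- Footnote that the pooled column covers two treatment periods against one for placebo.
- State in words where follow-up events, and any serious events reported after the Week 7 visit, are counted.

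This needs no new data: the SAP already uses onset, visit and last-dose dates. Where the last-dose date is incomplete, SAP 8.2 substitutes the drug-return date, so the split for those early stoppers is approximate. The cost is one column, one line and a footnote, hence slightly longer tables. The change restores 14 days each for placebo, 20 mg and 200 mg among completers. It does not remove the confounding of drug with fixed period order.
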